9.3.2 Restrictions and Concomitant Medications

Once the study has begun, the subjects will be instructed to take only the study medication(s) described in this protocol. If the subject takes any other medication during the study, the Investigator will record the necessary information.

Table 9.3.2-1: Restrictions and Concomitant Medications

[Redacted]	[Redacted]	[Redacted]
[Redacted]	[Redacted]	[Redacted]
[Redacted]	[Redacted]	[Redacted]
[Redacted]	[Redacted]	[Redacted]
[Redacted]	[Redacted]	[Redacted]
[Redacted]	[Redacted]	[Redacted]
[Redacted]	[Redacted]	[Redacted]
[Redacted]	[Redacted]	[Redacted]
[Redacted]	[Redacted]	[Redacted]
[Redacted]	[Redacted]	[Redacted]
[Redacted]	[Redacted]	[Redacted]
[Redacted]	[Redacted]	[Redacted]
[Redacted]	[Redacted]	[Redacted]
[Redacted]	[Redacted]	[Redacted]
[Redacted]	[Redacted]	[Redacted]
[Redacted]	[Redacted]	[Redacted]
[Redacted]	[Redacted]	[Redacted]
[Redacted]	[Redacted]	[Redacted]
[Redacted]	[Redacted]	[Redacted]

Subjects who violate any of the above restrictions may be excluded or dropped from the study at the discretion of the Investigator. Individual exceptions to the above restrictions may be approved by the Investigator.

9.3.3 Female Subjects of Childbearing Potential

A female subject is considered of childbearing potential (WOCBP) if she is not post-menopausal, not congenitally sterile; not diagnosed as infertile (and not undergoing treatment to reverse infertility); or has not undergone successful surgical sterilization (such as tubal ligation, bilateral oophorectomy, or hysterectomy) completed at least 3 months prior to Screening. A woman is considered of non-childbearing potential if she is post-menopausal (if she is either amenorrheal for greater than 2 consecutive years, or naturally post-menopausal [no mense] for at least 1 year), surgically sterile (tubal ligation, bilateral oophorectomy, or hysterectomy), congenital sterility, or diagnosed as infertile and not undergoing treatment to reverse infertility.

WOCBP must use effective methods of birth control starting at least 4 weeks prior to the Screening Visit 1 and until the last study procedure, such as total abstinence, intrauterine device, a double-barrier method, oral, transdermal, injected or implanted non- or hormonal contraceptive. A sterile sexual partner is not considered an adequate form of birth control. Subjects on hormonal contraceptives must have been on the same hormonal contraceptive for at least one month before the Screening Visit 1 and continue throughout the duration of the study.

WOCBP will be instructed to contact the Investigator immediately if they suspect they might be pregnant.

9.3.4 Male Subjects

Male subjects must commit to not father a child or donate sperm from the first dose until 3 months post-last dose.

Male subjects (with female partners of childbearing potential) must commit to the consistent and correct use of at least two effective methods of birth control (as listed below) or total abstinence from the Medical Screening Visit until 30 days after the last administration of the investigational product.

- Condom and diaphragm with spermicide (foam, cream, gel, sponge)
- Condom and cervical cap with spermicide (foam, cream, gel, sponge)
- Non-hormonal intrauterine device (IUD)

Female partner(s) of male volunteers also have the option to use the following highly effective hormonal method of contraception: implants, injectables, combined oral contraceptives, and IUDs.

10. STUDY PRODUCT AND TREATMENT SEQUENCE

10.1 Study Product and Treatment

The following products will be used in the study:

Product A: 0.25% Reproxalap Ophthalmic Solution (reproxalap) (Manufactured by Aldeyra Therapeutics, Inc.) administered 1 drop in each eye approximately 5 minutes prior to DEC entry.

Product B: Xiidra® (5% lifitegrast ophthalmic solution) (Manufactured by Novartis Pharmaceuticals Canada, Inc.) administered 1 drop in each eye approximately 5 minutes prior to DEC entry.

10.2 Treatment Sequence

At Visit 1, eligible subjects will be enrolled and scheduled for Visits 2 and 3. Subjects will be dosed as per a fixed sequence at Visits 2 and 3.

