4. STUDY SUMMARY

Study Title	An Exploratory, Single-Center, Double-Masked, Crossover Clinical Trial to Assess Safety and Tolerability of 0.25% Reproxalap Ophthalmic Solution Compared to Xiidra® in Subjects with Dry Eye Disease in a Dry Eye Chamber
Protocol Number	C1D01056
Study Phase	Phase 2
Study Objectives	To explore the safety and tolerability of reproxalap compared to Xiidra® in a dry eye chamber.
Study Endpoints	
Exploratory Endpoints:
 
 • Change in ocular discomfort score (0-10) from baseline over 45 minutes in the dry eye chamber • Change in ocular itching score (0-10) from baseline over 45 minutes in the dry eye chamber 
Safety Endpoints:
 
 • Snellen visual acuity (SVA) • Slit-lamp examination (SLE) • Adverse event (AE) query
Study Design	C1D01056 is an exploratory, single-center, double-masked, crossover design trial to assess the safety and tolerability of reproxalap compared to Xiidra® in subjects with Dry Eye Disease (DED). The clinical trial will consist of 3 visits to the clinic over a period of approximately 34 days. This study will be an investigator-initiated trial.
Study Products and Treatment	
Treatment Products
 
Product A: 0.25% Reproxalap Ophthalmic Solution (reproxalap) (Manufactured by Aldeyra Therapeutics, Inc.)
 
Product B: Xiidra® (5% lifitegrast ophthalmic solution) [REDACTED]
 
Treatment products (reproxalap or Xiidra®) will be dosed topically in both eyes and administered once (1 drop in each eye) approximately 5 minutes prior to dry eye chamber (DEC) entry.

Route of Administration	Ophthalmic (topical ocular administration of eye drops)
Study Population	Approximately 50 subjects with DED, ages 18 to 70 years, are expected to be enrolled in the trial. The study will consist of 1 treatment group.
Study Conduct	The clinical trial will consist of 3 visits. At each visit, staff will update the subjects' concomitant medication and collect AEs. A urine pregnancy test will be administered to all female subjects. Coronavirus Disease 2019 (COVID-19) screening questionnaire, oral temperature and COVID-19 rapid test will be performed at Visits 1, 2 and 3. Eligibility

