	
criteria will be reviewed. There will be at least 7 days of washout period following Visits 1 and 2.
 
I. Medical Screening- Visit 1 (Day -21 to -8)
 
All subjects will undergo a medical screening visit (Visit 1), including written informed consent, demographics, medical/medication and ocular history. Intraocular Pressure (IOP) will be performed prior to DEC entry. SVA and SLE will be performed prior to DEC entry. Symptom questionnaires (Ocular Discomfort Score, Ocular Itching Score) will be performed approximately 15 minutes pre-saline dose and approximately every 5 (+2) minutes while in the DEC. Saline will be administered in the clinic approximately 5 minutes prior to DEC entry. Following DEC exit (approximately 45 minutes), SVA (EDTRS), and SLE will be performed following chamber exit. Dilated fundoscopy will be performed post-DEC after SVA and SLE. After at least 7 days of washout, subjects will return for Visit 2.
 
II. Treatment- Visit 2 (Day 1 + 2) and Visit 3 (Day 8 + 2)
 
A fixed treatment sequence is allotted for Visit 2 and 3. SVA and SLE will be performed prior to symptom questionnaires, and eligibility criteria will be reviewed. Symptom questionnaires (Ocular Discomfort Score and Ocular Itching Score) will be performed approximately 15 minutes pre-dose and approximately every 5 (+2) minutes while in the DEC. Test product will be administered in the clinic approximately 5 minutes prior to chamber entry. Subjects will be exposed to a DEC (approximately 45 minutes) with Ocular Discomfort Score and Ocular Itching Score assessments every 5 (+2) minutes. SVA (EDTRS) and SLE will also be performed following DEC exit. There will be at least 7 days of washout after Visits 1 and 2. Dilated fundoscopy will be performed post-DEC after SVA and SLE at Visit 3.

Inclusion Criteria
	
 1. Eighteen (18) to 70 years of age at the time of screening (either gender and any race). 2. Ability to provide written informed consent. 3. Reported history of dry eye for at least 6 months prior to Visit 1. 4. Reported history of the use of eye drops within 6 months but not within 2 weeks of Visit 1. 5. [REDACTED]

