10.3 Masking and Unmasking

10.3.1 Masking

This is a double-masked clinical trial. The Sponsor (PI), Investigators, qualified site personnel (except delegated unmasked pharmacy staff), and subjects will be masked to the investigational product administered until database lock. Only the delegated unmasked pharmacy staff and Scientific Affairs staff involved with preparing the assignment of Treatment A and B to the fixed sequence will have access to the treatment under evaluation.

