10.3.2 Emergency Unmasking

Emergency unmasking should only be performed when necessary to treat the subject. Most often, knowledge of the possible treatment assignments is sufficient to treat a clinical trial subject who presents with an emergency condition.

The investigator should make every effort to contact the Medical Monitor to discuss the subject's emergency and the need to unmask prior to unmasking any subject.

In situations in which the investigator has tried but is unable to reach the Medical Monitor, best judgement on the part of the investigator should be used, based on the nature and urgency of the clinical situation, and may proceed with unmasking without having successfully reached and discussed the situation with the Medical Monitor. Once a subject's treatment assignment has been unmasked, the Medical Monitor should be notified within 24 hours of the unmasking of the treatment, without revealing the treatment.

As this is a fixed sequence clinical trial, every attempt will be made to maintain the masking for the other subjects in the event of an unmasking must occur, an unmasking procedure will be developed.

The emergency unmasking should be performed by the designated site personnel. The investigator must also indicate in source documents and the Case Report Form (CRF) that the mask was broken and provide the date, time, and reason for breaking the mask.

Any AE or Serious Adverse Event (SAE) associated with breaking the mask must be recorded and reported as specified in the protocol. The investigator has the responsibility to contact the

Sponsor (PI) in the event of a drug-related, serious, unexpected AE, the ProPharma Group or designee will be provided with the treatment assignment for the subject for regulatory reporting.

If treatment assignment is unmasked, the treatment will be discontinued immediately, and the subject will be discontinued from the clinical trial.

The mask may be broken in the case of pregnancy should the subject desire this information.

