11.2 Visit 1: Screening (Day -21 to -8)

The following activities will be completed at Visit 1:

- Subjects will be asked to sign and date the Informed Consent Form.
- Demographic data, including date of birth, age, race and ethnicity, will be recorded.
- Medical/Medication and Ocular history will be completed for each subject.
- A urine pregnancy test will be performed (for all female subjects). Subjects with a positive result will be excluded.
- The subjects will be evaluated for study inclusion, exclusion and restriction criteria.
- Symptom Questionnaires (Ocular Discomfort Score, Ocular Itching Score) will be performed within 15 minutes prior to DEC entry and every 5 +2 minutes up to 45 minutes while in the chamber.
- An SVA and SLE will be performed pre and post-DEC.
- IOP will be performed prior to DEC entry and dilated funduscopy will be performed post-DEC.
- Saline will be administered in the clinic approximately 5 minutes prior to the DEC entry.
- DEC session (approximately 45 minutes).
- Adverse events and concomitant medications will be recorded before the subject leaves the site.
- After 7 ± 1 day of washout period, eligible subjects will come to Visit 2

11.3 Visits 2 (Day 1 + 2) and 3 (Day 8 + 2): Treatment/Dry Eye Chamber

Eligible subjects will return for 2 treatment visits. The treatment visits will occur following at least 7 days after visits 1 and 2. At Visit 2 the subjects will be randomized to receive one of the 2 treatment sequences as mentioned in [Section 10.2](#). At Visits 2 and 3, the following activities will be performed:

- Medical/medication and ocular history will be updated for each subject.
- A urine pregnancy test will be performed (for all female subjects). Subjects with a positive result will be excluded.
- The subjects will be evaluated for study inclusion, exclusion and restriction criteria.
- An SVA and SLE will be performed pre and post-DEC.
- Symptom questionnaires (Ocular Discomfort Score, Ocular Itching Score) will be performed within 15 minutes prior to study treatment administration and approximately every 5 minutes while in the chamber.
- Test product will be administered in the clinic approximately 5 minutes prior to the DEC entry.
- DEC session (approximately 45 minutes).
- Dilated funduscopy will be performed post-DEC after SVA and SLE at Visit 3.
- Adverse events and concomitants medications will be recorded before the subject leaves the site.
- Study exit (Visit 3).

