15. ADMINISTRATIVE STUDY RECORDS

15.1 Subject Enrollment and Identification

Participants will be enrolled in the study prior to any screening procedures being performed. All participants will be assigned a unique subject identification number. This number will be used to identify their records until they are randomized into a fixed treatment sequence. Participants who

are randomized into the study will be assigned a unique randomization number which will be used to identify their records post-randomization.

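### The protocol describes both one fixed treatment order and randomization to two orders; under the fixed order, reproxalap versus Xiidra cannot be separated from Visit 2 versus Visit 3

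*Combined protocol and SAP*

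**What the plan says.** The current text describes the treatment order in two incompatible ways.

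**One fixed order**
- Section 10.2: "Subjects will be dosed as per a fixed sequence at Visits 2 and 3".
- Section 4, Study Conduct: "A fixed treatment sequence is allotted for Visit 2 and 3". Section 4, Study Population: "The study will consist of 1 treatment group".
- Section 10.3.1 gives access to the code only to unmasked pharmacy staff and the staff "preparing the assignment of Treatment A and B to the fixed sequence will have access to the treatment under evaluation". The sequence is in the singular.
- Section 10.3.2: "As this is a fixed sequence clinical trial, every attempt will be made to maintain the masking for the other subjects".

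**Randomization**
- Section 11.3: "At Visit 2 the subjects will be randomized to receive one of the 2 treatment sequences", with a reference to Section 10.2.
- Table 5.1-1 has a randomization row at Visit 2. Section 14.2 tabulates adverse events from randomization onward. Section 16.4 ties kit numbers to a randomized assignment.

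**Both at once**
- Section 15.1 uses a subject number "to identify their records until they are randomized into a fixed treatment sequence".

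No section lists the possible sequences or an allocation ratio. Section 14.1 names no analysis model, so nothing is said about visit effects. Sections 4 and 8.1 call the design a crossover.

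**The concern.** Two competent sites could run different trials from this protocol: one with every subject in the same order, the other with subjects split between two orders. That defect needs no assumption.

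The choice decides whether the objective can be met. Section 7.1 sets a single objective, the safety and tolerability of reproxalap compared with Xiidra. With one order, anything that differs between Visit 2 and Visit 3 is attributed to product. Examples are habituation to the chamber, practice with the rating scale, or a change in chamber response over time. More subjects do not remove this bias.

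The schedule also makes the two visits unequal for safety. Adverse events are queried at each return visit (Section 12.2.7), so the Visit 2 product is followed until Visit 3. After Visit 3 the subject exits, and the follow-up call in Section 11.4 covers only early withdrawals. Fundoscopy after active treatment happens only at Visit 3. Under one order, the same product always has the shorter observation window and is always the one just given before fundoscopy.

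A shared order also weakens the mask. Anyone who learns one subject's code can infer both visits for every subject.

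**Working it through.** **Inputs.** From the documents: 50 subjects (Section 9.1); saline at Visit 1; one product at each of Visits 2 and 3; symptom scores from 0 to 10. The documents give no SD, visit effect, test, alpha or dropout rate, and no basis for the 50, so there is no plan figure to reproduce. The SDs, shifts and completer numbers below are assumptions.

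**Step 1: is the product difference estimable?** Take response = subject + visit + product. The A-minus-B contrast is estimable only if appending it to the design matrix leaves the rank unchanged.

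| Data used | Order | Columns | Rank | Rank with contrast | A minus B |
|---|---|---|---|---|---|
| Visits 2 and 3 | all one order | 52 | 51 | 52 | not estimable |
| Visits 2 and 3 | 25 AB, 25 BA | 52 | 52 | 52 | estimable |
| Visits 1 to 3 | all one order | 54 | 52 | 53 | not estimable |
| Visits 1 to 3 | 25 AB, 25 BA | 54 | 53 | 53 | estimable |

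The saline session does not help, because each visit then has its own product.

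**Step 2: what does each design estimate?** Let visit effect mean Visit 2 minus Visit 3, and let each product's carryover act at the next visit.
- All subjects A first: mean A minus B = (A − B) + visit effect − carryover of A.
- All subjects B first: mean A minus B = (A − B) − visit effect + carryover of B.
- AB/BA with a period term averages the two: (A − B) − (carryover of A − carryover of B)/2. The visit effect cancels.

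**Step 3: size under one order.** Assume one summary change score per subject per visit, a two-sided 5% paired t-test and no true product difference. The rejection rate comes from the non-central t with ncp = shift/(SD/√n). At SD 2.0 and n = 50, SD/√n = 2.0/√50 = 0.283, so shifts of 0.25, 0.5 and 1.0 point give ncp of 0.88, 1.77 and 3.54.

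| n | SD of difference | Shift 0.25 | Shift 0.5 | Shift 1.0 |
|---|---|---|---|---|
| 50 | 1.5 | 21.1% | 63.7% | 99.6% |
| 50 | 2.0 | 13.9% | 41.0% | 93.4% |
| 50 | 2.5 | 10.7% | 28.4% | 79.2% |
| 45 | 2.0 | 13.0% | 37.5% | 90.7% |
| 40 | 2.0 | 12.0% | 33.8% | 86.9% |

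Smaller n lowers the rejection rate only because the test is weaker. The bias equals the whole shift at any n.

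**Step 4: check by simulation** (40,000 trials, SD 2.0, n = 50, the same three shifts). One order: 14.1%, 41.1%, 93.4%. AB/BA with a period term: 5.1%, 4.9%, 5.1%.

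**Step 5: precision.** For AB/BA, SE = 0.5 × SD × √(1/n₁ + 1/n₂).
- 25:25 at SD 2.0: √(0.08) = 0.283, the same as the paired analysis. The 95% half-widths are 0.569 and 0.568.
- 20:25 completers: √(0.09) = 0.300, against 2.0/√45 = 0.298. The half-widths are 0.605 and 0.601.

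**The case against.** **Two preset orders.** Section 15.1 could mean that each subject is randomized to one of two preset orders. That fits Section 11.3, Table 5.1-1 and Section 16.4, and a single treatment group is a natural description of a crossover in which everyone receives both products. The reading is possible. It sits poorly with the singular in Section 10.3.1, and worse with Section 10.3.2, which treats unmasking one subject as a threat to the others because the sequence is fixed. Even if it is right, Sections 4, 10.2, 10.3.1 and 10.3.2 are then wrong and need changing.

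**A difference can still be computed.** True: the mean difference between Visits 2 and 3 exists under one order. It is a product effect only if there is no visit effect and no carryover, and the trial cannot test that.

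**Design features limit visit effects.** Subjects have a full saline chamber session first, each visit has its own pre-dose score, the stated washout is at least 7 days (although Section 11.2 gives 7 ± 1), and by Visit 2 subjects have been off their own drops for about three weeks. These features may shrink a visit effect. Change from baseline removes shifts in the pre-dose level, but not a change in how subjects respond to the chamber.

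**The trial is exploratory and plans no test.** This stands against reading the percentages as forecasts. It does not rescue the comparison, which is the only objective. Section 13.1 also allows the report to go into regulatory submissions.

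**Masking has safeguards.** Section 10.3.2 limits who unmasks and tells the site not to reveal the treatment to the Medical Monitor. One break therefore does not automatically unmask everyone. The procedure that would contain a break is still deferred: "an unmasking procedure will be developed". Not printing the order is reasonable if there is only one; not listing the possible sequences when Section 11.3 refers to them is not.

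**Conclusion.** The point holds. The contradiction is certain and lies in unredacted current text. The aliasing is conditional on the fixed-order wording, which is the better supported reading; under it the loss is exact, since the product difference cannot be estimated separately from visit at any sample size.

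The false-positive figures illustrate the consequence. At n = 50 and SD 2.0 they are about 14%, 41% and 93% for visit shifts of 0.25, 0.5 and 1.0 point, with ranges of 11% to 21%, 28% to 64% and 79% to 99.6% across SDs of 2.5 down to 1.5. They rest on an assumed test, SD, shift and summary score. The conclusion does not depend on them. This must be fixed before subjects are dosed.

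**What to change.** 1. Rewrite Section 10.2: subjects are randomized 1:1 in blocks at Visit 2 to A-then-B or B-then-A. The reference from Section 11.3 then works.
2. Remove the fixed-sequence and one-group wording from Section 4 and from Sections 10.3.1, 10.3.2 and 15.1.
3. In Section 14.1 and the synopsis, state that the within-subject product difference is estimated with a period term, and state the assumption of no differential carryover. The bias is half of any difference in carryover. Because that assumption leans on the washout, reconcile the two washout statements (at least 7 days, and 7 ± 1 days in Section 11.2).
4. Write the unmasking procedure into Section 10.3.2.
5. If the order can no longer be changed, state that product is confounded with visit, report results by visit descriptively, and make no comparative claim.

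**Cost:** a randomization list, pharmacy preparation of two orders, and an amendment with IRB approval. Sections 15.1 and 16.4 mention randomization numbers and uniquely numbered kits, but these are among the conflicting passages, so whether they are in place must be confirmed. No extra subjects or visits are needed. One degree of freedom is lost, and the standard error is essentially unchanged if completers are roughly balanced between orders.

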10.3 Masking and Unmasking

10.3.1 Masking

This is a double-masked clinical trial. The Sponsor (PI), Investigators, qualified site personnel (except delegated unmasked pharmacy staff), and subjects will be masked to the investigational product administered until database lock. Only the delegated unmasked pharmacy staff and Scientific Affairs staff involved with preparing the assignment of Treatment A and B to the fixed sequence will have access to the treatment under evaluation.

